#### 1.1.9.6Sample Size

Based on a previous study (Calais et al, 2017), we anticipate that 53% of patients will undergo an implemented change in management after F-DCFPyL PET/CT. Based on our previous experience and interim analysis, due to incomplete patient data, especially low turn-in rate from referring treating physician for post PET/CT intended treatment (Questionnaire 2), a sample size of 400 patients would provide >90% power to determine whether the proportion of patients implementing change in management exceeds 40%, assuming an exact binomial test, and a one-sided alpha of 0.025. A sample size of 400 patients is expected to produce a margin of error for the proportion of patients implementing change in management ranging from 6.9%, assuming a two-sided 95% confidence level. Sample size calculation was conducted in collaboration with the UCLA Department of Biostatistics ([name], [name]).

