# 1 Clinical Protocol

# 1.1 IMPACT OF F-DCFPyL PET/CT ON INITIAL AND SUBSEQUENT TREATMENT STRATEGIES OF PATIENTS WITH PROSTATE CANCER (PROSPYL).

# 1.1.1 BACKGROUND AND RATIONALE

Prostate cancer is the most commonly diagnosed cancer and second leading cause of cancer death in American men (Edwards et al., 2014). Imaging and staging of prostate cancer is critical for treatment planning. Existing conventional imaging (CT, MRI and bone scans) has a low sensitivity in detecting local recurrence or metastatic disease. Choline based PET tracers are commonly used because of their affinity to prostate cancer but their diagnostic capability is limited, and they cannot reliably identify local recurrence, lymph node involvement, or soft-tissue deposits (Evangelista et al., 2013; Perera et al., 2016). Gallium-68 labeled HBED-CC PSMA (more commonly called Ga-PSMA-11) has been shown to be superior to choline based PET agents for the staging of prostate cancer, both Carbon11 and Fluorine-18 compounds (Afshar-Oromieh et al., 2014; Morigi et al., 2015; Schwenck et al., 2017). PSMA is expressed on the majority of prostate cancer cells, and is an ideal cell membrane protein to image. The detection rate of PSMA-11 for metastatic lesions in patients with recurrent prostate cancer is high: 50% for patients with a PSA less than 1 ng/ml, and above 85% for patients with a PSA greater than 2 ng/ml (Eiber et al., 2015; Perera et al., 2016). Several studies have reported a high impact on management of patients with biochemical recurrence after curative primary treatment with a rate of management change of 61%, 53%, 62%, 76% (Albisinni et al., 2017; Hope et al., 2017; Roach et al., 2017; Sterzing et al., 2016). In two studies, the impact on management was lower for initial staging indication: 26% and 21% (Roach et al., 2017; Sterzing et al., 2016). Limitations of Ga-PSMA-11 PET imaging include: a) rapid urinary excretion resulting in intense bladder accumulation obscuring the prostate region, 2) the requirement of local radionuclide generators for labeling 3) shorter half-life and reduced spatial resolution as compared to F agents. Recently developed second-generation PSMA PET probes using an F label, for example F-DCFPyL, overcome these limitations of Ga-based tracers. Preliminary studies have shown that F-DCFPyL to be promising for evaluation of metastatic prostate cancer. Therefore, we intend to perform a separate analysis of initial versus subsequent management as management options are considerably different (curative versus salvage/palliative).

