# 1.1.3 STUDY SYNOPSIS

This is a prospective, Phase II, open-label study in patients with prostate cancer. Study participants will receive intravenous administration of F-DCFPyL and undergo a PET/CT imaging study. Patients may be reenrolled in the study, if F-DCFPyL PET/CT is performed for subsequent management decision.

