# 1.1.3.3 Endpoints Primary

#### **Endpoint:**

Intended and implemented management changes after F-DCFPyL PET/CT assessed separately for initial and subsequent treatment decisions.

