# 1.1.4 INCLUSION EXCLUSION CRITERIA

#### Inclusion criteria

- 1. Patients who fulfill criteria for initial staging or restaging as outlined below:
- 1) Initial treatment strategy decisions (initial staging)

All patients with histologically proven prostate cancer or strong suspicion of prostate adenocarcinoma based on very high PSA levels (>50 ng/mL) who require an initial treatment/management decision who may be candidate for any of the following strategies:

- A) Surgery
- B) External radiation therapy (RT) C) Other focal therapies
- D) Systemic medical treatment E)

Watchful waiting

- 2) Assessment for Subsequent treatment strategy (restaging), any of the following:
  - A) Patients with biochemical recurrence who are potential candidates for any salvage treatment. Biochemical recurrence is defined by rising PSA after definitive therapy with prostatectomy or radiation therapy, as any of the following:
    - a. Post radical prostatectomy (RP): PSA equals to or greater than 0.2 ng/mL measured more than 6 weeks after RP
    - b. Post-radiation therapy: Nadir + greater than or equal to 2 ng/mL rise in PSA
  - B) Patients with known prostate cancer who undergo restaging because of new symptoms
  - C) Patients with known metastatic prostate cancer who undergo restaging because of rising PSA with negative or inconclusive conventional imaging
  - D) Patients with known prostate cancer who are treated medically or with RLT in whom response to treatment is assessed
- 2. Capability to provide written informed consent
- 3. Able to remain still for duration of each imaging procedure (about 30 minutes)
  - \* Patients may be reenrolled in the study, if F-DCFPyL PET/CT is performed for subsequent management decision.

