#### 1.1.8.4 Measurements

#### 1) Primary Outcome Measurement:

A separate analysis of initial versus subsequent management will be performed.

The principal goal of this study is to evaluate the impact of F-DCFPyL PET/CT on patient management in patients with prostate cancer. The study includes a total of 3 questionnaires; Questionnaires 1 and 2 will be collected from referring physicians prior to and just after completion of the imaging study; these are designed to determine the intended patient management before and intended management changes after PET/CT.

Patients can only be enrolled in the study if the pre-PET questionnaire (Q1) is completed.

*Treatment Modality Analysis*: 3 categories of management changes will be evaluated:

- o no change
- Inter-modality management changes (Major), i.e. change in modality or addition/removal of one or more modalities in the overall management

- Intra-modality management changes (Minor), i.e. same modality before and after PSMA PET/CT, however for instance:
  - Changes in Medical treatment
  - Changes in radiation approach
  - Changes in surgical approach
  - Addition/removal of concomitant ADT

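### The >90% power in section 1.1.9.6 rests on one overall 53% change rate from a recurrence setting, so it does not describe the by-group primary endpoint, and the evaluable number behind it is unclear

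*Combined protocol and SAP*

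**What the plan says.** Section 1.1.9.6 (Sample Size) states "we anticipate that 53% of patients will undergo an implemented change in management after" the scan. It claims more than 90% power with 400 patients to show that the implemented-change proportion exceeds 40%, using an exact binomial test at one-sided alpha 0.025, and gives a 95% margin of error of 6.9%. It introduces the figure of 400 with "Based on our previous experience and interim analysis, due to incomplete patient data", mentioning low return of Questionnaire 2, but gives no evaluable number.

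The primary endpoint (section 1.1.3.3) is management change "assessed separately for initial and subsequent treatment decisions". Section 1.1.8.4 repeats this: "A separate analysis of initial versus subsequent management will be performed". Section 1.1.9.2 plans analysis of the whole cohort and of each group.

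Section 1.1.1 reports "high impact on management of patients with biochemical recurrence after curative primary treatment with a rate of management change of 61%, 53%, 62%, 76"%, and says that "the impact on management was lower for initial staging indication: 26% and 21"%. The reference matching the citation in 1.1.9.6 is, by its title, a study of biochemical recurrence. Section 1.1.4 also admits restaging indications for which no change rate is cited, for example "Patients with known prostate cancer who are treated medically or with RLT in whom response to treatment is assessed".

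Section 1.1.9.3 plans descriptive statistics for management change and names neither a test nor an interval. Section 1.1.9.5 specifies Wilson 95% intervals for positive predictive value.

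**The concern.** The sample-size statement answers a different question from the primary endpoint. It covers one pooled proportion, while the endpoint is two proportions that the protocol's own background expects to differ widely. The pooled rate depends on how many initial-staging patients enrol, and that share is not stated. At the cited initial-staging rates, the initial group would lie below the 40% threshold.

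No decision rule is tied to 40%, so the loss is one of justification and precision. A reader cannot tell whether 53% is a reasonable overall rate for the enrolled mix, how many patients will contribute data, or how precisely either group's rate will be estimated.

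**Working it through.** **Inputs.** From 1.1.9.6: p0 = 0.40, p1 = 0.53, n = 400, exact binomial, one-sided alpha 0.025, margin 6.9%. From 1.1.1: initial-staging rates 0.26 and 0.21; recurrence rates 0.53, 0.61, 0.62 and 0.76. Assumed, because the documents do not give them: the initial share f, and an evaluable number of 400 or 200.

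**1. The plan's power.** Take the smallest r with P(X ≥ r | n, 0.40) ≤ 0.025; power is P(X ≥ r | n, p).
- n = 400: r = 180, attained alpha 0.0238, power at 0.53 = 99.9%. The >90% claim holds.
- n = 200: r = 95, attained alpha 0.0188, power at 0.53 = 94.8%.

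**2. The plan's margin.** Half-width = 1.96 × √(p(1−p)/n).
- n = 400, p = 0.53: 1.96 × √(0.2491/400) = 4.9 points, not 6.9.
- Solving for 6.9 points: n = 1.96² × 0.2491/0.069² = 201.

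The margin therefore matches about 200 patients, a number the documents never state.

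**3. Overall rate needed for 90% power.** 48.08% with 400 evaluable; 51.78% with 200.

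**4. Tolerable initial share.** The overall rate is f × p_init + (1 − f) × p_sub, so the largest f that keeps 90% power is (p_sub − p_needed)/(p_sub − p_init). For example, with 400 evaluable: (0.53 − 0.4808)/(0.53 − 0.26) = 0.182.

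| Subsequent rate | 400 evaluable, initial 26% / 21% | 200 evaluable, initial 26% / 21% |
|---|---|---|
| 53% | 18% / 15% | 4.5% / 3.8% |
| 61% | 37% / 32% | 26% / 23% |
| 62% | 39% / 34% | 28% / 25% |
| 76% | 56% / 51% | 48% / 44% |

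As one point in that range, take a 25% initial share with 53% in subsequent patients. The overall rate is 46.3% / 45.0%, and power is 71% / 52% with 400 evaluable or 39% / 26% with 200.

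The opposite case: 0.25 × 0.26 + 0.75 × 0.62 = 0.53, which reproduces the plan's rate exactly.

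**5. By group.**
- Initial group at a true rate of 26%: the chance of rejecting 40% is about 0.03% with 20 patients and smaller still at the larger sizes examined (40 to 300).
- Subsequent group at 53%: power is 89.2% with 163 evaluable and 90.6% with 164 (r = 79), and stays at or above 90% from there up to 400.
- Half-widths at a 30/70 split:
  - 400 evaluable: initial (n = 120, 26%) 7.8 points; subsequent (n = 280, 53%) 5.8 points.
  - 200 evaluable: initial (n = 60, 26%) 1.96 × √(0.1924/60) = 11.1 points; subsequent (n = 140, 53%) 1.96 × √(0.2491/140) = 8.3 points. Power for that subsequent group is 87%.

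**The case against.** The strongest defence is that this is an open-label Phase II study with a descriptive primary analysis, by-group reporting already planned, and a power statement that is correct as written. The whole cohort is also one of the planned analysis sets, so a pooled calculation is not out of place. The cited rates are proxies: the 53% source and the other change rates with visible titles concern the gallium-labelled tracer, and one initial-staging source measured management intent by its title rather than implemented change. These points stand, and they limit the consequence to reporting and precision. They do not remove the gap: if the analysis is descriptive, precision for the by-group endpoint is what should justify the size, and none is given. The 53% is itself a proxy of the same kind.

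Three stronger readings are tempting and not supported.
- That 53% is wrong or the trial underpowered. The documents' own rates can yield 53% overall, and at 61% or 62% among subsequent patients a sizeable initial share is tolerable.
- That only 200 patients will be evaluable. That number is inferred from the margin alone.
- That the 40% test was chosen after the interim analysis. The section mentions that analysis when explaining incomplete data and the size of 400; it does not date the threshold or the test.

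The source match also rests on a title. The in-text year is 2017, the listed year is 2018, and section 1.1.1 credits its 53% to other citations, though also in recurrence.

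**Conclusion.** The point holds as a missing justification, not as an arithmetic error in the power. The >90% figure is right at its own inputs but depends on an overall rate that no stated mix supports, and it does not carry over to the by-group primary endpoint. At the cited initial-staging rates the initial group has essentially no power to exceed 40%; the subsequent group has at least 90% power at 53% only if at least 164 of its patients are evaluable.

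The evaluable number matters as much as the mix. Moving from 400 to 200 raises the overall rate needed for 90% power from about 48.1% to 51.8%, and at a 53% subsequent rate cuts the tolerable initial share from 18% / 15% to 4.5% / 3.8%. The 6.9% margin and 400 patients cannot both describe the same analysis set.

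These figures assume the cited rates apply to this tracer and to implemented change, and that patients are independent, although "Patients may be reenrolled in the study". Mix and evaluable number are assumptions throughout.

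**What to change.** In section 1.1.9.6:
- State the population behind the 53%.
- Restate the power either for the subsequent group (at least 90% at 53% needs at least 164 evaluable subsequent patients) or as conditional on the overall rate and the actual evaluable number. Reconcile that number with the 6.9% margin.
- Give the expected 95% interval half-width for each group at the projected or observed group sizes. With 200 evaluable and a 30/70 split, for illustration, these are about 11 points (initial, at 26%) and 8 points (subsequent, at 53%).

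In section 1.1.9.3:
- Report the implemented-change rate with a Wilson 95% interval for each group, as 1.1.9.5 already does for predictive value. Treat the whole-cohort rate as descriptive and dependent on the mix.
- If the exact binomial test against 40% is kept, carry it over from 1.1.9.6, say which group it applies to, and state whether it was specified before or after the interim analysis.

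The cost is protocol wording and a count of patients by group, with no added patients or procedures. The drawback is that the stated power becomes conditional and less favourable.

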#### Disease stage based management Analysis:

Treatment management will also be categorized as follow: A/ Local Prostate Fossa therapy, B/ Regional Pelvic therapy, C/ Lombo-aortic LN focused therapy, D/ Solitary LN or oligometastatic disease focused therapy and E/ Metastatic disease systemic therapy.

Management change will be classified as: 1/ no change or 2/ change (addition/removal of one or more of these disease stage based treatment strategies)

Questionnaire 3 will be mailed to referring physicians 3-6 months after completion of the imaging study to determine whether intended management changes were implemented.

To assess the implemented treatment management, following methods will be used, in descending priority:

- 1. Systematic electronic chart review when available
- 2. Questionnaire
- 3. Referring physician contact (email, phone or fax)
- 4. Patient contact (email, phone or fax)

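### Enrolling 400 patients does not address selective return of Questionnaire 2, and the plan has no missing-data rule for intended management change, part of the primary endpoint

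*Combined protocol and SAP*

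**What the plan says.** All references are to the combined protocol and SAP.

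- **Endpoint (1.1.3.3).** The primary endpoint has two components: "Intended and implemented management changes after" the scan, assessed separately for initial and subsequent treatment decisions.
- **How intended change is measured (1.1.8.1, 1.1.8.4).** Q1 records the plan before the scan and is a condition of enrolment. Q2 records the plan after the scan and is due from the referring physician within 4 weeks. Intended change is the difference between the two.
- **Other sources.** Section 1.1.8.4 ranks four sources, with chart review first, but introduces them with "To assess the implemented treatment management, following methods will be used, in descending priority". There is no such list for intended change. Section 1.1.8.1 adds that management changes will be verified by chart review and telephone interview, without saying that this stands in for a missing Q2.
- **Analysis (1.1.9.2, 1.1.9.3).** Endpoints are analysed in the whole cohort and in the two treatment groups, using descriptive statistics. Nothing is said about missing questionnaires.
- **Sample size (1.1.9.6).** Drawing on earlier experience and an interim analysis, the section reports incomplete data, especially "low turn-in rate from referring treating physician for post PET/CT intended treatment (Questionnaire 2"), and gives this as a reason for 400 patients. The figures attached to that number concern implemented change: "we anticipate that 53% of patients will undergo an implemented change in management after" the scan, tested for "whether the proportion of patients implementing change in management exceeds 40" per cent.

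**The concern.** Because Q1 is mandatory, the loss occurs after the scan, when the referring physician knows the PET result. Physicians may return Q2 more readily when the scan changed their plan, or less readily. Either pattern makes the rate among returned forms differ from the rate among all scanned patients.

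Allowing for incomplete data in the sample size protects precision and power, but not against selective return. As the plan stands, the intended-change result would in practice be a rate among responders. Its confidence interval would narrow as enrolment grew while any bias stayed the same, and no planned analysis would show whether responders and non-responders differ.

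**Working it through.** **Inputs.** From 1.1.9.6, all for implemented change: expected proportion 0.53, reference proportion 0.40, N = 400, "assuming an exact binomial test, and a one-sided alpha of 0.025", and a margin of error "ranging from 6.9%, assuming a two-sided 95% confidence level". The Q2 return rate r is described as low, with no figure, so r = 40% to 80% is assumed here. No expected rate or threshold is given for intended change. The 0.53 is borrowed below only to put numbers into the formulas.

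**1. The plan's own figures.** The plan says "a sample size of 400 patients would provide >90% power". With N = 400, the exact test rejects at 180 or more changes (exact one-sided alpha 0.0238), and power at 0.53 is 99.94%. The claim is met. With 200 evaluable patients the test rejects at 95 or more, and power is 94.8%.

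The margin of error at N = 400 is 1.96 × √(0.53 × 0.47 / 400) = 4.9%, not 6.9%. Solving for n gives 1.96² × 0.53 × 0.47 / 0.069² ≈ 201. That is consistent with about half of 400 being evaluable, but the text does not say so.

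**2. Bias of the responder-only rate.**

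Bias = (1 − r) × (rate in responders − rate in non-responders)

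N does not appear. For example, with r = 0.50, responders at 53% and non-responders at 40%, the bias is 0.50 × 0.13 = 6.5 points. Holding r at 50%:

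| N enrolled | Q2 returned | Margin of error among responders | Bias in this example |
|---|---|---|---|
| 200 | 100 | 9.8% | 6.5 points |
| 400 | 200 | 6.9% | 6.5 points |
| 800 | 400 | 4.9% | 6.5 points |

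**3. Bounds that need no assumption about why forms are missing.**

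Lower bound (no missing case changed) = 0.53r

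Upper bound (every missing case changed) = 0.53r + (1 − r)

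| Return rate r | Lower | Upper | Width = 1 − r |
|---|---|---|---|
| 40% | 21.2% | 81.2% | 60 points |
| 50% | 26.5% | 76.5% | 50 points |
| 60% | 31.8% | 71.8% | 40 points |
| 70% | 37.1% | 67.1% | 30 points |
| 80% | 42.4% | 62.4% | 20 points |

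The width depends only on r, so it does not rest on the borrowed 53%. It is the same at any N. Sampling error comes on top.

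**The case against.** The strongest reply has four parts.

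1. **The powered quantity is implemented change.** Both 53% and 40% belong to it, and it has four ranked sources, so it is less exposed to Q2 loss. This stands. A reader might infer from the bounds that spanning 40% would overturn the trial's conclusion, or that the type I error of its test is inflated. The documents do not support that, because they set no threshold and no test for intended change. Even on the borrowed figures, the lower bound exceeds 40% once r is above 0.40 / 0.53 ≈ 75%.
2. **Enrolment is not the only measure.** Section 1.1.8.1 provides for verification by chart review and telephone interview, and does not limit this to implemented change. It would therefore be wrong to say that nothing else is planned. But the sentence does not say that verification replaces a missing Q2, and 1.1.9.6 still treats low return as a reason for the sample size.
3. **Allowing for incomplete data in a sample size is ordinary practice.** Agreed; the gap lies in the analysis sections. A reader might also infer that N was raised from a smaller number. That is a reasonable reading, but no earlier N is given.
4. **Bias is not demonstrated.** Correct, and its direction is unknown. The point needs only that a larger N cannot remove it and that the planned analysis would not reveal it.

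It is also tempting to say that missing Q2 forms can simply be completed from the chart. Later entries may show what was done rather than what was intended within 4 weeks of the scan, which would merge two components that 1.1.3.3 lists separately. Section 1.1.8.4 itself limits chart review to where a chart is available.

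**Conclusion.** The point holds for intended management change and should be addressed. The plan reports that Q2 is often missing, gives this as a reason for N = 400, and specifies neither a denominator nor a missing-data analysis for the component that depends on Q2.

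The exposure is a range as wide as the non-return share: 20 points at 80% return, 50 at 50% and 60 at 40%. The locations of the bounds rest on the borrowed 53%; the return rates are assumptions because the documents give none. The 6.9% margin hints at about half being evaluable but does not establish a 50% return rate.

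The conclusion does not extend to implemented change or to the comparison with 40%, and it does not assert that bias is present.

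**What to change.** Amend 1.1.9.2 and 1.1.9.3 for intended change, overall and in each treatment group:

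1. State the denominator. Report the Q2 return rate by group (initial, subsequent) and by PET result.
2. Present the rate among returned forms together with an estimate weighted by the inverse probability of Q2 return. Model return on the Q1 plan, PSA, group and PET result, and allow for clustering by referring physician where this is recorded. This estimate assumes that return is unrelated to intended change given those variables.
3. Add no-change and all-change bounds over all scanned patients, which do not need that assumption.
4. Use chart documentation of post-scan intent only as a labelled sensitivity analysis, restricted to entries dated within the 4-week Q2 window, so that intended and implemented change remain distinct.

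**Cost.** Items 1 to 3 are modest extra analysis, mainly of data the protocol already collects. Item 4 requires some new chart abstraction if it is done. Reported uncertainty for intended change will be wider. No additional patients or visits are needed.
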